#### **6.1 Inclusion Criteria**

- 1) Primary chronic constipation meeting the Rome III criteria with  $\leq$ 2 mean weekly CSBMs (CSBM refers to the bowel movement without the help of drug or hands within the past 24 hours with the feeling of complete evacuation. The bowel movement beyond 24 hours after the use of medicine/hands also could be considered an SBM) in the past three months. They should conform to at least one of the following items at the same time: a) a feeling of straining during evacuation (at least once per 4 bowel movements); b) lumpy or hard stools (at least once per 4 bowel movements); c) a feeling of incomplete evacuation after a bowel movement (at least once per 4 bowel movements); e) needing the help of hands for evacuation (at least once per 4 bowel movements).
- 2) Conditions for the diagnosis of irritable bowel syndrome (IBS) are inadequate.
- 3) Previous laxative use failed to provide satisfactory relief.
- 4) Participants aged 18 to 75 years old.
- 5) Two or fewer CSBMs per week during the 2-week baseline assessment (run-in) period.
- 6) No use of medicine for constipation during the 2 weeks before enrolment (except rescue medication usage); no acupuncture treatment for constipation in the previous 1 month; no participation in any other on-going trial.
- 7) Volunteered to join this trial and signed the informed consent.

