#### **6.3 Subject Withdrawals**

The participants may leave the study at their own discretion, or the experts from the gastrointestinal or anorectal department in each site may determine that it is the best for the subject to discontinue participation (due to worsening of symptoms, or the occurrence of a serious adverse event).

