#### 10. Subject Evaluations and Outcomes

#### 10.1 Baseline Evaluations

Outcomes contain the complete spontaneous bowel movements (CSBMs), spontaneous bowel movements (SBMs), stool consistency (according to Bristol Stool Scale), straining during the defecation, rescue medicine used, and the form of Chinese-version Patient Assessment of Constipation Quality of Life (PAC-QOL). Participants will record their bowel movements, constipation-related symptoms, medicine used for constipation every day through week -2, week -1, weeks 1-8, weeks 11-12, weeks 15-16, weeks 19-20, and weeks 31-32. In both groups, participants without bowel movements (BMs) for 3 or more consecutive days were allowed to use bisacodyl (5-10mg a day before bedtime, Boehringer Ingelheim) or 110 ml glycerol enema as rescue medicine with documentation (time, dosage, and frequency of use) in the stool diary.

The SBMs are the bowel movements that occur in the absence of rescue medicine, or other assistant methods (laxatives, enemas, suppositories usage, or digging out by fingers) within the preceding 24 hours, which include the CSBMs. When participants used rescue medicine, or other measures for constipation, the defecation within 24 hours was considered a non-spontaneous bowel movement, whereas defecation exceeding 24 hours was deemed an SBM. CSBMs were the SBMs with the sensation of complete evacuation.

Outcome record time point: Baseline (the last day of week -2 and week -1), week 2, week 4, week 6, week 8, week 12, week 16, week 20, and week 32 (Figure 1).

[figure not shown]
Outcome assessing time frame: baseline period (weeks -2 to week -1), the latter 6-week treatment (weeks 3-8), the first 2-week treatment (weeks 1-2), and the follow-up periods (weeks 11-12, weeks 15-16, weeks 19-20, weeks 31-32).

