- 7) Time to the first CSBMs, which was the time from the first treatment to the first CSBMs counting by days. Rescue medicines are not allowed to be used during 48 hours before and after the first treatment. If the first CSBM had not occurred yet, and rescue medicines were used in the condition of no BM in a succession of three or more days, the BM occurs within 24 hours after the use of rescue medicine will not be regarded as CSBM, and the days-counting will continue till the occur of the first CSBM.
- 8) The change from baseline of the score of PAC-QOL at week 4 and week 8. PAC-QOL is a self-report questionnaire to evaluate the quality of life in participants with constipation, which was distributed by Mapi Research Trust in France. This questionnaire contains 28 items including 4 basic parts of physical discomfort, worries and concerns, psychosocial discomfort, and satisfaction. We use the Chinese version in our trial16. Assessing point: baseline, week 4 and week 8.
- 9) The proportion of participants using rescue medicine (bisacodyl or glycerol enema) and the mean weekly dosage of rescue medicine used ((bisacodyl or glycerol enema) over weeks 1-2, 3-8, 11-12, 15-16, 19-20, 31-32. Assessing time frame: baseline, weeks 1-2, 3-8, 11-12, 15-16, 19-20, 31-32.

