### 13.3 General Principles of Statistical Analysis

The primary outcome was one-tailed test at significance levels of 0.025. All the other statistical analyses were two-tailed tests, at a significant level of 0.05, using SAS software, version 9.4 (SAS Institute Inc, Cary, North Carolina, USA). For measurement data, mean±standard deviations (M±SD), median, minimum, maximum, were presented. Differences between groups were compared using group t tests or nonparametric tests. Comparisons with the baseline used paired t tests or nonparametric tests. For counting data, cases and percentages were presented, and differences between groups were compared using Chi-squared tests, Fisher's exact probabilities or non-parameters tests. For abnormal distributed data, differences between groups were compared using nonparametric tests. Missing data for the primary outcome were imputed using the multiple imputation (MI) method under the missing at random assumption for the mITT population. The results for the PP set were used as the sensitivity analysis for the multiple imputation. For secondary outcomes, no imputation was used and observed data were used for analyzing.

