#### 13.6 Secondary Outcomes

- (1) For the proportion of participants with 3 or more mean weekly CSBMs, the Cochran-Mantel-Haenszel (CMH) test, stratified by center, was used to test a hierarchical comparison between two groups. Assessing timeframe: weeks 1-2, 11-12, 15-16, 19-20, 31-32.
- (2) For the proportion of participants with ≥1 increase of mean weekly CSBMs from baseline, the Cochran-Mantel-Haenszel (CMH) test, stratified by center, was used to test a hierarchical comparison between two groups. Assessing timeframe, weeks 1-2, 3-8, 11-12, 15-16, 19-20, 31-32.
- (3) For the change from baseline in mean weekly CSBMs, a repeated measures analysis of variance was used, setting group, time, and the interaction of group and time as the fixed effects; besides, the baseline CSBMs data and usage of rescue medicine were set as the covariate. Assessing timeframe: weeks 1-2, 3-8, 11-12, 15-16, 19-20, 31-32.
- (4) For the change from baseline in mean weekly SBMs, the same statistical analysis was conducted in accordance with the change from baseline in mean weekly CSBMs. Assessing timeframe: weeks 1-2, 3-8, 11-12, 15-16, 19-20, 31-32.
- (5) For the mean scores of straining, the Wilcoxon rank-sum test was used. Assessing timeframe: weeks 1-2, 3-8, 11-12, 15-16, 19-20, 31-32.
- (6) For the mean scores of stool consistency, the Wilcoxon rank-sum test was used. Assessing timeframe: weeks 1-2, 3-8.
- (7) For the time to the first CSBM (counting by days), the Wilcoxon rank-sum test was used.
- (8) For the change in mean scores of PAC-QOL between two groups, t test was used. Assessing time point: week 4 and week 8.
- (9) Rescue medicine usage: For the proportion of participants using rescue medicine (bisacodyl or glycerine enema), the Chi-square test was used. For the average dosage of bisacodyl or glycerine enema used per week, the Wilcoxon rank-sum test was used. Assessing timeframe: weeks 1-2, 3-8, 11-12, 15-16, 19-20, 31-32.

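### Time to first CSBM has no end of observation and no rule for participants without a CSBM; read literally, the planned test compares speed only among those who had one

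*Supplement*

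**What the plan says.** - **Definition.** SAP section 10.3, item 7: "Time to the first CSBMs, which was the time from the first treatment to the first CSBMs counting by days". If rescue medicine is used before the first CSBM, "the days-counting will continue till the occur of the first CSBM". The final protocol, section 2.4.7.3, item 7, has the same open-ended rule. Neither document gives a last day of observation, a censoring date, or a value or rank for someone who never has a CSBM.
- **Test.** SAP section 13.6, item 7: "For the time to the first CSBM (counting by days), the Wilcoxon rank-sum test was used".
- **Missing values.** SAP section 13.3: "For secondary outcomes, no imputation was used and observed data were used for analyzing".
- **Level.** SAP section 13.3: "All the other statistical analyses were two-tailed tests, at a significant level of 0.05".
- **Diary coverage.** SAP section 10.1 has daily records in "weeks 1-8, weeks 11-12, weeks 15-16, weeks 19-20, and weeks 31-32", after the two run-in weeks. Recording is continuous only to the end of week 8.
- **Population.** SAP section 6.1 requires "Two or fewer CSBMs per week during the 2-week baseline assessment (run-in) period", so zero is allowed, and also that earlier laxatives gave no satisfactory relief. SAP section 6.3 allows experts at the site to end participation "due to worsening of symptoms, or the occurrence of a serious adverse event".

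No Kaplan-Meier, log-rank, Cox or other method for censored times appears in the final protocol or the SAP.

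**The concern.** A time-to-event outcome needs a rule for people who do not have the event. Here some are to be expected: the entry criteria admit people with no CSBM at run-in, and participants may leave before a first CSBM. Three provisions then act together. The definition gives these people no number, the missing-data rule gives them no substitute, and an ordinary rank-sum test has no way to use a censored time.

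What remains is a comparison of speed among those who had a CSBM, a group formed after randomisation by the outcome itself. Participants with no CSBM have the worst result on this outcome, yet they carry no weight. If one arm had more of them, this analysis would not show it.

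**Working it through.** **1. The plan's own figures.** None is given for time to first CSBM. The only planned sizes are for the primary outcome (SAP section 9), and they reproduce:

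n = (1.645 + 0.845)² × [0.3167 × 0.6833 + 0.309 × 0.691] / (0.3167 − 0.309 + 0.1)² = 6.2001 × 0.42992 / 0.011599 = 229.80, rounded up to 230.

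230 × 1.2 = 276. The recruitment target is 560, so 560 / 2 = 280 per arm, the size used below.

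**2. What each test can see.** Let qA and qB be the shares who have a CSBM by day 56, and let timing among them be the same in both arms.

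- *Observed times only.* The test compares a random A participant with a random B participant, given that both had a CSBM. With equal timing, the chance that A is earlier is 1/2 (ties split) whatever qA and qB are. Its rejection rate is therefore the nominal 5%.
- *Non-events ranked last, tied.* The chance that A is earlier, counting ties as one half, is qA·qB/2 + qA(1 − qB) + (1 − qA)(1 − qB)/2 = 1/2 + (qA − qB)/2. With 30% v 15% never having a CSBM, this is 1/2 + (0.70 − 0.85)/2 = 0.425. With 5% v 3% it is 1/2 + (0.95 − 0.97)/2 = 0.49.

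**3. Simulation.** Assumptions: 280 per arm, exponential time to first CSBM with mean 8 days among those who have one, cut-off at day 56, two-sided 0.05, no early withdrawal, log-rank test not stratified. The chance that an eventual event falls after day 56 is exp(−56/8) = 0.0009, so the assumed never-rate drives the result. The share without a CSBM is an assumption throughout, because the documents give none.

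| Never-rate, A v B | Analysed if observed only, A v B | Observed-only Wilcoxon | Wilcoxon, non-events last | Log-rank, censored at day 56 |
|---|---|---|---|---|
| 30% v 15% | 196 v 238 | 5.6% | 88% | 97% |
| 20% v 10% | 224 v 252 | 6.1% | not run | 82% |
| 20% v 15% | 224 v 238 | 4.8% | 18% | 29% |
| 10% v 5% | 252 v 266 | 6.2% | 18% | 41% |
| 5% v 3% | 266 v 272 | 5.4% | 7% | 12% |
| 20% v 20% | 224 v 224 | 5.3% | not run | 5.9% |

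The analysed numbers are 280 × (1 − never-rate). Each row rests on 1,000 runs, except 20% v 10% and 20% v 20% (1,500). The Monte Carlo standard error at 5% with 1,000 runs is √(0.05 × 0.95 / 1,000) = 0.7 points. A separate set of 600 runs per scenario gave log-rank 97%, 84%, 42% and 13% for 30% v 15%, 20% v 10%, 10% v 5% and 5% v 3%, with the observed-only test at about 4% to 6%.

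**4. The opposite case: equal never-rates and a true speed difference (mean 8 v 10 days).** In the order of the last three columns, rejection was 58%, 45% and 28% at 10% never in both arms, and 54%, 33% and 17% at 20% (1,000 runs). Here the log-rank test is the weakest.

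**5. Can the direction reverse?** Only with a further assumption. With mean 10 days and never-rates of 10% v 25%, the observed-only test rejected in 4.9% of runs. If the arm with 10% is also made slower among those with a CSBM (mean 13 v 10 days), it rejected in 62%, always in favour of the arm with more non-events.

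**The case against.** The strongest reply is that no sentence in the SAP says these participants are left out. Someone with a complete 56-day diary and no CSBM does have information: the time exceeds 56 days. A rank-sum test could place all such people last, as ties, without imputing a number, and the wording that counting goes on until a CSBM occurs fits that reading as well as it fits dropping them. This stands in part. Exclusion is the literal result of reading sections 10.3, 13.3 and 13.6 together, but it is an inference. The alternative is an unwritten rule, which would leave the handling to be chosen after the data are seen.

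A reader might infer that the Wilcoxon test itself is the fault. It is not: ranking non-events last recovers most of the power at 30% v 15% (88% against 97%), and the log-rank test is weaker for a purely early difference in speed. The fault is the missing rule for non-events.

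A reader might also infer that the gaps in the diary after week 8 defeat any rank test. They do not. A first CSBM after week 8 may not be datable, but it is known to be later than every event in weeks 1-8, and a rank test needs only that order. It must still be told to use it.

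Last, this is one of nine secondary outcomes, and an excess of non-responders would show in the primary responder proportion, the other responder proportions and the change in CSBMs. That limits the consequence, but it does not make this comparison valid.

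**Conclusion.** The point holds in this form: as written, the plan gives no end of observation and no place in the analysis to participants without a CSBM, so the literal comparison is of speed among those who had one. Under equal timing it has about 5% rejection whatever the difference in never-rates, against about 13% (5% v 3%) to 97% (30% v 15%) for a log-rank test with censoring. These figures rest on assumed never-rates and exponential times. If few participants lack a CSBM, or the shares are similar in the two arms, the effect is minor.

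A reader might go further and conclude that the worse arm would look faster. The documents do not support that: it needs the added assumption that the arm with fewer non-events is slower among those who respond. Nor is the primary non-inferiority conclusion touched, since this outcome does not enter it. The change should be made, but it is a correction to a secondary analysis.

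**What to change.** In SAP sections 10.3 and 13.6, item 7:

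- State that observation for this outcome ends at day 56.
- Censor participants without a CSBM at their last completed treatment-period diary day, at most day 56.
- Present Kaplan-Meier curves by arm with a log-rank test stratified by centre.
- Report the number and share without a CSBM in each arm, separating those with a full diary from those who left early.

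If early speed is the main interest, a Wilcoxon-type test that keeps everyone in is acceptable instead: a Gehan-Wilcoxon test for censored times, or the rank-sum test with non-events ranked last. Choose one in advance and state it. Ranking last also needs a stated rule for people who leave before day 56. Censoring them assumes that leaving is unrelated to the prospect of a CSBM, which is doubtful when the reason is worsening symptoms, so reasons should be tabulated.

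The cost is a few lines of SAP text and a standard procedure call. The diary dates are already collected. The price in power is the log-rank test's weaker performance when arms differ only in early speed (28% against 58% for the observed-only test in the 8 v 10 day example with 10% never in both arms).

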### 4. Randomization

After the baseline assessment has been carried out and the informed consent has been obtained, eligible participants will be randomized, stratified by enrollment centers, to the EA group or the prucalopride group with the ratio of 1:1. The random numbers will be obtained by the acupuncturists through the Central Randomization System by phone or website. Randomization will be performed centrally with varied blocks by the Clinical Evaluation Centre of the China Academy of Chinese Medical Sciences in Beijing using the PROC PLAN program of SAS 9.3 software, and the random scheme generator will not take any part in the statistical analysis. The randomizing scheme and related parameters was called the blind codes, which will be sealed by the generator and stored by a special researcher. Except for the most senior system administrator, no one has the access to the random scheme in the central random system.

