#### 10.3 Secondary Outcomes

- 1) The proportion of participants with 3 or more mean weekly CSBMs over weeks 1-2, 11-12, 15-16, 19-20, 31-32. The EA group was discontinued after 8 weeks of treatment, while the drug group continued to take prucalopride for 24 weeks in the absence of QT interval elongation or other severe cardiac adverse events (like myocardial infarction, severe arrhythmia, etc.). Assessing time frame: weeks 1-2, weeks 11-12, 15-16, 19-20, 31-32
- 2) The proportion of participants with  $\geq 1$  increase of mean weekly CSBMs from baseline over weeks 1-2, 3-8, 11-12, 15-16, 19-20, 31-32. Assessing time frame: baseline, weeks 1-2, weeks 3-8, weeks 11-12, 15-16, 19-20, 31-32.
- 3) The change from baseline in mean weekly CSBMs over weeks 1-2, 3-8, 11-12, 15-16, 19-20, 31-32. Assessing time frame: baseline, weeks 1-2, weeks 3-8, weeks 11-12, 15-16, 19-20, 31-32.
- 4) The change from baseline in mean weekly SBMs over weeks 1-2, 3-8, 11-12, 15-16, 19-20, 31-32. Assessing time: baseline, weeks 1-2, weeks 3-8, weeks 11-12, 15-16, 19-20, 31-32.
- 5) The change from baseline in the mean score of stool consistency of each SBM over weeks 1-2 and weeks 3-8. Assessing time: baseline, weeks 1-2 and weeks 3-8. Participants will self-report their stool consistency of each SBM according to the 7-type BSFS (scored by 1 to 7 respectively).

- Type 1: Separate hard lumps, like nuts (hard to pass)
- Type 2: Sausage-shaped, but lumpy
- Type 3: Like a sausage but with cracks on its surface
- Type 4: Like a sausage or snake, smooth and soft
- Type 5: Soft blobs with clear cut edges (passed easily)
- Type 6: Fluffy pieces with ragged edges, a mushy stool
- Type 7: Watery, no solid pieces. Entirely liquidz
- 6) The change from baseline in the mean score of straining of each SBM over weeks 1-2, weeks 3-8, weeks 11-12, 15-16, 19-20, 31-32. Assessing time: baseline, weeks 1-2, 3-8, 11-12, 15-16, 19-20, 31-32. Participants will self-report their straining degree of each SBM in the defecation diaries according to the following scale:
  - 0 = not difficult;
  - 1 = a little difficult, need some straining to defecate;
  - 2 = difficult, need straining to defecate;
  - 3 = very difficult, need hard straining to defecate.

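### SAP 13.6 tests straining and stool consistency as mean scores although both are defined as change from baseline, and several secondary analyses leave out the collected baseline score or the stratifying centre

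*Supplement*

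**What the plan says.** **Outcome definitions.** SAP 10.3(6) defines the straining outcome as "The change from baseline in the mean score of straining of each SBM". SAP 10.3(5) defines stool consistency in the same way, and protocol 2.4.7.3(5)-(6) agrees. PAC-QOL in SAP 10.3(8) is "The change from baseline of the score of PAC-QOL", at weeks 4 and 8. Rescue use in 10.3(9) is a proportion and a mean weekly dosage per period, not a change.

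**Tests in SAP 13.6.**
- (5): "For the mean scores of straining, the Wilcoxon rank-sum test was used". Item (6) says the same for stool consistency.
- (8): "For the change in mean scores of PAC-QOL between two groups, t test was used".
- (9): "For the proportion of participants using rescue medicine (bisacodyl or glycerine enema), the Chi-square test was used". Weekly rescue dosage gets a Wilcoxon rank-sum test.
- (3)-(4): repeated-measures models for CSBM and SBM change, with baseline and rescue use as covariates. No centre term is named.

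**Design.** SAP 4 states that "eligible participants will be randomized, stratified by enrollment centers". SAP 10.1 lists straining, consistency, rescue use and PAC-QOL among the baseline evaluations. SAP 13.5 and 13.6(1)-(2) use a centre-stratified CMH test. SAP 13.3 gives only general rules (t, nonparametric and chi-square tests), and protocol 7.3 applies CMH to the primary outcome alone, so no general rule supplies the missing terms.

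**The concern.** There are two separate issues.

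The first is consistency. Items (3), (4) and (8) of SAP 13.6 speak of change; items (5) and (6) do not. A programmer working from 13.6 would compare follow-up scores, while one working from 10.3 would compare changes. These are different quantities, and the text leaves the choice open until data are in hand.

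The second is efficiency. The trial collects baseline scores and stratifies by centre, and the SAP already uses a centre stratum for some outcomes and a baseline covariate for others. For PAC-QOL, straining, consistency and rescue use it does not carry this through, and it gives no reason. What is at stake is precision. These are two-sided difference tests ("All the other statistical analyses were two-tailed tests, at a significant level of 0.05"), so an imprecise comparison is more likely to end in an uninformative absence of difference.

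**Working it through.** **The plan's own figure.** The only sample size in the documents is for the primary outcome (SAP 9): (1.645 + 0.845)² × [0.3167 × 0.6833 + 0.309 × 0.691] / 0.1077² = 229.8, so 230 per group, and 230 × 1.2 = 276. Both figures reproduce. Neither bears on this point: no power, SD or correlation is stated for the secondary outcomes.

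**Wording of 10.3 against 13.6.**

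| Outcome | Defined in 10.3 as | Tested in 13.6 as |
|---|---|---|
| Straining | change | mean score |
| Stool consistency | change | mean score |
| PAC-QOL | change | change |

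**Baseline covariate.** Let rho be the correlation between baseline and follow-up, and k = SD(baseline)/SD(follow-up). Neither is in the documents, so both are assumptions. In units of the follow-up variance, the variance of the treatment comparison is:
- follow-up score alone: 1
- change score: 1 + k² − 2·rho·k, which is 2(1 − rho) when k = 1
- ANCOVA: 1 − rho²

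With k = 1:

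| rho | Change | ANCOVA | Cut against change | Cut against raw score | Extra n, change score | Extra n, raw score |
|---|---|---|---|---|---|---|
| 0.3 | 1.40 | 0.91 | 35% | 9% | 54% | 10% |
| 0.5 | 1.00 | 0.75 | 25% | 25% | 33% | 33% |
| 0.7 | 0.60 | 0.51 | 15% | 49% | 18% | 96% |

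Extra n is the additional number of participants needed to match ANCOVA. For an effect with 80% power on raw scores, power on change is 66%, 80% and 95%, and with ANCOVA 84%, 90% and 97.5%, at rho 0.3, 0.5 and 0.7.

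These formulas describe means. For rank tests, a simulation (224 per arm, that is 280 × 0.8; normal data; 1,500 runs) gave power of 79/78/78% for the rank-sum test on raw scores, 65/77/94% on change, and 82/87/96% for a rank ANCOVA. That rank ANCOVA regressed follow-up ranks on baseline ranks, and real scores are bounded (0-3 and 1-7), so this is indicative only.

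**Sensitivity to k.** Change-score variance minus ANCOVA variance is (1 + k² − 2·rho·k) − (1 − rho²) = (k − rho)². At k = rho it is zero: with rho = 0.5 and k = 0.5, both variances are 0.75. The comparison with raw scores does not depend on k.

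**Centre.** Assume a share ICC of the variance lies between centres. Under stratified allocation:
- true two-sided alpha of the unadjusted test = 2[1 − Φ(1.96/√(1 − ICC))]
- power with centre in the model, from a nominal 80% = Φ(2.80/√(1 − ICC) − 1.96)

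| ICC | Alpha, unadjusted | Power with centre |
|---|---|---|
| 0.01 | 0.049 | 80.4% |
| 0.02 | 0.048 | 80.8% |
| 0.05 | 0.044 | 82.0% |
| 0.10 | 0.039 | 84.0% |

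The gain from 80% is an upper value. Stratified allocation already balances the centres, so the unadjusted test's actual power is Φ(0.84/√(1 − ICC)), which is 81.2% at ICC 0.10. The gain there is then about 2.7 points rather than 4.

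**The case against.** The strongest reply is that the chosen tests are valid and fixed in advance for each outcome, and that using every available covariate on supportive outcomes is a preference. Validity stands: an unadjusted randomised comparison is not biased, and leaving out centre makes the test conservative. What the reply does not explain is why the rescue-use proportion is handled differently from the other proportions, or PAC-QOL change differently from CSBM change.

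Mean scores in 13.6(5)-(6) may be shorthand for change, since 10.3 sits in the same document. That is possible, but item (8) of the same list writes out the change, so the text needs settling.

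Several stronger readings are tempting and are not supported:
- *PAC-QOL ignores baseline.* It does not. The change score uses baseline by subtraction; only the covariate is missing.
- *Rescue use should be adjusted for baseline.* SAP 10.3(9) does not define it as a change. The case there is for centre alone.
- *Testing raw scores loses precision against testing change.* With equal variances, change is the less precise of the two when rho is below 0.5. The mismatch is one of definition.
- *The plan wastes a fixed share of its sample, say one third.* That figure needs rho = 0.5 and, against change scores, equal variances. Entry is restricted by symptoms that include straining and hard stools (SAP 6.1), so equal variances cannot be taken for granted.

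**Conclusion.** The point holds in two parts. The difference between SAP 13.6(5)-(6) and the definitions in SAP 10.3 and protocol 2.4.7.3 is plain on the text and needs no assumption. The missing baseline and centre terms are also plain on the text, but their cost can only be given as a range.

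The baseline covariate is the larger part. The 15-35% and 9-49% variance reductions rest on rho between 0.3 and 0.7, and the first of them also on equal variances; it shrinks as the SD ratio approaches rho. Centre is the smaller part: at most about 0.4 to 4 power points for ICC 0.01 to 0.10, with no inflation of the false-positive rate. The variance ratios do not apply to rescue use, where the argument is agreement with the stratified design.

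A reader might infer that the trial's main conclusion is at risk. It is not: the primary non-inferiority comparison is already stratified by centre and is unaffected. This is a change that should be made, not one on which the trial depends.

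**What to change.** - **SAP 13.6(5)-(6):** state that the analysed quantity is change from baseline, as in 10.3. Use one prespecified rank-based ANCOVA of change, with baseline score and centre. Do not add a switch of test that depends on how the data look; SAP 13.6 now fixes one test, and that should be kept.
- **13.6(8):** PAC-QOL change at weeks 4 and 8 by ANCOVA with treatment, baseline score and centre.
- **13.6(9):** rescue-use proportion by CMH stratified by centre; rescue dosage by the van Elteren test stratified by centre.
- **13.6(3)-(4):** add centre to the repeated-measures models.

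One detail goes with the first item. Straining and consistency are scored per SBM, so a participant with no SBM in the run-in has no baseline score, and SAP 13.3 imputes nothing for secondary outcomes. The SAP should say how such participants are handled.

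The cost is SAP wording and minor programming. Baseline scores and centre are already collected, and neither the sample size nor the primary analysis changes.

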- (10) Post-hoc analyses: A weekly CSBM responder was defined as a patient who had ≥3 CSBMs for a given week and an increase from baseline of ≥1 CSBM for that same week. An overall CSBM responder was a patient who was a weekly CSBM responder for at least 6 of the 8 treatment weeks (75%). A sustained CSBM responder met the overall responder criteria, and also met the responder criteria for at least 3 of the last 4 treatment weeks. For proportion of the overall CSBM responder and sustained CSBM responder over weeks 1-8, Chi-square tests were used. For the weekly CSBMs and its changes from baseline of each week for data collection (week -2, week -1, weeks 1-8, weeks 11-12, weeks 15-16, weeks 19-20, weeks 31-32), a repeated measures analysis of variance was used, setting group, time, and the interaction of group and time as the fixed effects; besides, the baseline CSBMs data and usage of rescue medicine were set as the covariate.
- (11) For the acceptability of EA, the number and proportion of participants who accepted the treatment of electroacupuncture was describe.

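### The post-hoc weekly CSBM model (SAP 13.6, item 10) uses run-in weeks -2 and -1 both as responses and as the baseline covariate, which shrinks the group main effect to 16/18 and confuses the group-by-time test

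*Supplement*

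**What the plan says.** SAP 13.6, item (10), is labelled post-hoc. Besides two responder definitions, it plans a model of weekly CSBMs and of their change from baseline.

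- **Responses:** "For the weekly CSBMs and its changes from baseline of each week for data collection (week -2, week -1, weeks 1-8, weeks 11-12". The list continues with weeks 15-16, 19-20 and 31-32.
- **Model:** "a repeated measures analysis of variance was used", "setting group, time, and the interaction of group and time as the fixed effects". No covariance structure is named.
- **Covariates:** "the baseline CSBMs data and usage of rescue medicine were set as the covariate".

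SAP 10.1 gives the baseline window as "baseline period (weeks -2 to week -1"). It does not write out how the two weeks are combined into one value.

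SAP 13.6, item (3), covers change from baseline in mean weekly CSBMs. It uses the same fixed effects and covariates, but its listed times begin at weeks 1-2 and include no run-in week.

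**The concern.** Read together, 13.6(10) and 10.1 put the same two diary weeks on both sides of one model: as two of the response times and as the baseline covariate. One of the two outcomes is, in addition, change from those weeks. Neither group has been treated by then, so these responses carry no information on treatment. Item (3) avoids this, and item (10) gives no reason for differing.

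The weekly model gives the most detailed picture of how quickly an effect appears and how long it lasts, and persistence over 3 to 6 months is a stated objective (SAP 1 and 13.1). Three outputs are at stake: the size of the reported group main effect, the meaning of the group-by-time test, and the weekly standard errors.

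**Working it through.** The SAP states no figure for this model, so there is none to reproduce. The check is algebra, followed by simulation for the parts that need assumed data.

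**Inputs.** Response weeks from 13.6(10): 2 run-in + 8 treatment + 4 × 2 follow-up = 18, of which 16 follow randomisation. Baseline window from 10.1. Total of 560 participants, 1:1, from SAP 9. Assumption: baseline B = (y₋₂ + y₋₁)/2, with both run-in weeks recorded.

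**1. Redundancy.**
- The run-in changes are y₋₂ − B = (y₋₂ − y₋₁)/2 and y₋₁ − B = −(y₋₂ − y₋₁)/2. They sum to zero for every participant and have correlation −1.
- The 18 × 18 covariance of the change scores therefore has rank 17. A numerical check gave rank 17 and a smallest eigenvalue of zero to rounding. With the run-in weeks removed, the rank is 16 of 16 and the smallest eigenvalue about 0.98.
- For raw counts, y₋₂ + y₋₁ = 2B. The covariate fixes the sum of the two weeks; their difference stays free. One dimension is lost, not two.
- With a single baseline slope common to all weeks, the raw-count residual covariance has full rank away from slope 1, but its log-determinant falls without bound as the slope nears 1: 3.75 at slope 0, −10.1 at 0.999, −23.9 at 0.999999. On the change scale the slope is the raw-scale slope minus 1, so the same degenerate point lies at slope 0. An unstructured fit breaks down on either scale.
- A compound-symmetry fit to the raw counts converged normally.

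**2. Group main effect.** Let M be a participant's mean over the 16 post-randomisation weeks. The 18-week mean is (2B + 16M)/18 = B/9 + (8/9)M. Since B is already in the model, the group coefficient is exactly 8/9 of the 16-week coefficient, and so is its standard error. In one simulated trial of 560:

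| | 18 weeks | 16 weeks | Ratio |
|---|---|---|---|
| Estimate | 0.487 | 0.548 | 0.889 |
| Standard error | 0.0503 | 0.0566 | 0.889 |
| t | 9.675 | 9.675 | 1 |

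Over 500 simulated trials with a true effect of 0.25, the mean estimates were 0.2225 and 0.2503, and the rejection rate was 98.6% for both.

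**3. Group by time.** Suppose the effect is a constant Δ in all 16 post-randomisation weeks. The expected group difference is 0 in the run-in weeks and Δ afterwards, with an 18-week average of (16/18)Δ. The deviations from that average are −(16/18)Δ in two weeks and +(2/18)Δ in sixteen. Their sum of squares is 2(16/18)²Δ² + 16(2/18)²Δ² = 1.78Δ². With only the 16 weeks modelled it is 0. In a simulation with 280 per arm, assumed counts, compound symmetry and a constant effect (estimated at 0.494 on 16 weeks and 0.439 on 18), the interaction test rejected in about 90% of trials with the run-in weeks and about 4% without them.

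**4. Weekly standard errors.** Inclusion criterion 5 (SAP 6.1) caps run-in CSBMs at two per week, so run-in weeks can be expected to vary less than treated weeks. With assumed SDs of 0.7 (run-in) and 1.6 (treated) and within-patient correlation 0.5, the compound-symmetry total variance and weekly standard error √(4 × variance/560) were:
- 18 weeks: 1.218 + 0.285 = 1.502, giving 0.104.
- 16 weeks: 1.300 + 0.365 = 1.665, giving 0.109.
- Week-by-week regression, for comparison: 0.109.

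The shortfall is about 5%. Simulations with assumed counts also gave about 5%, with a nominal 5% weekly test rejecting in 6.2% to 6.4% of trials, against 4.7% to 5.2% without the run-in weeks.

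**The case against.** The strongest reply is that little depends on this model. It is post-hoc, the primary outcome is tested by CMH (SAP 13.5), and items (1) to (4) already cover early and late response without run-in weeks among their analysed times. The SAP names no covariance structure, averaging of the run-in weeks is inferred, and the week list may have been meant only as the list of weeks to display. Modelling baseline as a response is also an accepted approach in itself.

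Most of this stands, and it limits the reach of the point. The last argument does not rescue item (10), because the accepted approach does not also enter the same baseline as a covariate. If the list was meant for display, the sentence still assigns those weeks to the model and should say otherwise.

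Some stronger readings are tempting but are not supported:
- *The model cannot be fitted.* Only an unstructured covariance fails, and the SAP does not specify one.
- *The treatment comparison loses power.* With complete data the estimate and its standard error shrink together, so t and p do not move.
- *The weekly differences are diluted.* Week-specific contrasts come from group by time and are not averaged with the run-in weeks.
- *The covariate determines both run-in responses.* It fixes only their sum.

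**Conclusion.** The double use of weeks -2 and -1 is a real specification fault, on the plain wording of 13.6(10) and 10.1. Its consequences differ in certainty.

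- **By algebra:** the equally weighted main-effect estimate falls by 2/18 = 11.1%, and a constant effect registers as interaction. The interaction test therefore cannot be read as evidence of a changing effect after treatment starts.
- **Given that baseline is the mean of the two weeks:** the change-score covariance is singular, which matters only if an unstructured form is chosen.
- **Given a pooled-variance structure and quieter run-in weeks:** weekly standard errors are somewhat too small. The 5% figure, the weekly error rates and the 90% interaction rejection rate all depend on assumed data.

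The unchanged main-effect test holds for complete data. Missing weeks, or rescue use entered as a time-varying covariate, would break the exact cancellation. The primary analysis is untouched. This is a minor point, worth correcting because correction is so cheap.

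**What to change.** In item (10), limit the responses to weeks 1-8, 11-12, 15-16, 19-20 and 31-32, in line with item (3). Keep baseline CSBMs as a covariate, defined as the mean over weeks -2 and -1, and show those two weeks descriptively in the table or figure. It would help to name the covariance structure in the same sentence.

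The cost is one sentence in the SAP. No new data or additional analysis is needed, and no between-group information is lost, because the two weeks precede randomisation.
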